### 7.6.3 Compliance of EXTREME Regimen

Administration of cisplatin/carboplatin, 5-FU, and cetuximab will be witnessed by the investigator and/or study staff. Compliance with these reference therapies will be documented in the medical record and monitored by MSD or its designee.

## 7.7 Concomitant Therapy

Medications or vaccinations specifically prohibited in the exclusion criteria are not allowed during the study. If there is a clinical indication for any medication or vaccination specifically prohibited, discontinuation from study treatment may be required. The investigator should discuss any questions regarding this with the MSD Clinical Director. The final decision on any supportive therapy or vaccination rests with the investigator and/or the participant's primary physician. However, the decision to continue the participant on study treatment requires the mutual agreement of the investigator, MSD, and the participant.

### 7.7.1 Permitted Medications

All treatments that the investigator considers necessary for a participant's welfare may be administered at the discretion of the investigator in keeping with the community standards of medical care. All concomitant medication will be recorded on the eCRF including all prescription, over-the-counter (OTC) products, herbal supplements, and IV medications and fluids. If changes occur during the study period, documentation of drug dosage, frequency, route, and date should also be included on the eCRF.

All concomitant medications received within 28 days prior to the first dose of study treatment and up to 30 days after the last dose of study treatment should be recorded. Concomitant medications administered 30 days after the last dose of study treatment should be recorded for SAEs and events of ECIs as defined in Section 9.3. If a participant enters into Second

Course Phase, all concomitant medications received within 30 days before the first dose of Second Course study treatment should be recorded. Following Second Course Phase Safety Follow-up Visit, record all medications taken for SAEs and ECIs as defined in Section 9.3.

### 7.7.2 Restricted Medications

Listed below are specific restrictions for concomitant therapy during the course of the study:

- Use of coumarin-based anticoagulants (eg, warfarin) with epacadostat is discouraged. Low-dose warfarin (1 mg) is acceptable; however, other higher doses are discouraged. If an alternative to coumarin-based anticoagulants cannot be used, the INR should be monitored closely per SoC when epacadostat is started.

Note: For participants randomized to either the EXTREME arm or pembrolizumab monotherapy arm, the use of coumarin-based anticoagulants is not restricted.

- Use of any restricted medications as described in local package inserts or prescribing information for pembrolizumab, cetuximab, cisplatin, carboplatin, and/or 5-FU.

### 7.7.3 Prohibited Medications and Measures

Participants are prohibited from receiving the following therapies during the Screening and Treatment Phase of this study unless otherwise noted below:

- Any investigational medication other than the study treatments
- Antineoplastic systemic chemotherapy or biological therapy
- Immunotherapy not specified in this protocol
- Chemotherapy not specified in this protocol
- Systemic glucocorticoids for any purpose other than to modulate symptoms from an AE. The use of physiologic doses of corticosteroids may be approved after consultation with MSD. Additionally, a short, limited course of steroids may be used to treat medical conditions and/or AEs during the study after MSD notification and consultation.

Note: For participants randomized to the EXTREME arm the use of systemic glucocorticoids on study treatment is acceptable and may be required for premedication.

Note: Inhaled steroids are allowed for management of asthma/chronic obstructive pulmonary disease.

Note: Use of prophylactic corticosteroids to avoid allergic reactions (eg, to IV contrast dye) is permitted.

- Oncologic surgery for tumor control.
- Radiation therapy

- Administration of a live attenuated vaccine within 30 days before the first dose of study treatment and while participating in the study. Examples of live vaccines include, but are not limited to, the following: measles, mumps, rubella, varicella/zoster, yellow fever, rabies, BCG, and typhoid vaccine. Seasonal influenza vaccines for injection are generally killed virus vaccines and are allowed; however, intranasal influenza vaccines are live attenuated vaccines and are not allowed.

Note: For participants randomized to the EXTREME arm the use of live vaccines is acceptable during the study.

- Any MAOI or drug associated with significant MAO inhibitory activity is prohibited from 21 days before starting study treatment through 2 weeks after the final dose of epacadostat has been taken. See Appendix 7 for prohibited agents.

Note: For participants randomized to either the EXTREME arm or pembrolizumab monotherapy arm, the use of MOAI or drug associated with significant MAO inhibitory activity is acceptable during the study.

- Any UGT1A9 inhibitor, including: acitretin, amitriptyline, androsterone, cyclosporine, dasatinib, diclofenac, diflunisal, efavirenz, erlotinib, flutamide, gefitinib, gemfibrozil, glycyrrhetic acid, glycyrrhizin, imatinib, imipramine, ketoconazole, linoleic acid supplements, mycophenolic acid, niflumic acid, nilotinib, phenobarbital, phenylbutazone, phenytoin, probenecid, quinidine, ritonavir, sorafenib, sulfapyrazone, valproic acid, and verapamil.

Note: For participants randomized to the EXTREME arm or pembrolizumab monotherapy arm, the use of UGT1A9 inhibitors is acceptable.

The exclusion criteria describe other medications that are prohibited in this study. There are no prohibited therapies during the Post-treatment Follow-up Phase.

Participants who, in the assessment by the investigator, require the use of any of the aforementioned treatments for clinical management should be removed from the study.

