### 3.3.4 Benefit/Risk of EXTREME

Benefits and risks of the EXTREME regimen are summarized in Section 3.2.4. The EXTREME regimen demonstrated the significant increase in PFS and OS in first line head and neck cancer compared with chemotherapy (platinum + 5-FU). A total of 82% of patients experienced a Grade 3 or 4 AE including neutropenia (22%), anemia (13%), and thrombocytopenia (11%). These AEs occurred in similar frequencies to platinum-5-FU-treated participants [Vermorken, J. B., et al 2008]. Additional details regarding specific benefits and risks for EXTREME-treated participants may be found in the prescribing information for these SoC treatments.

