#### **Prior/Concomitant Therapy**

12. Has received prior systemic therapy (as part of multimodal treatment) for HNSCC administered in the recurrent and/or metastatic setting for incurable disease.

Note: Systemic therapy (as part of multimodal treatment) which was completed more than 6 months prior to signing consent if given as part of multimodal treatment for locally advanced disease is allowed.

13. Has not fully recovered (ie,  $\leq$ Grade 1 or at baseline) from AEs due to a previously administered treatment.

Note: Participants with  $\leq$ Grade 2 alopecia are an exception to this criterion and may qualify for the study.

Note: If participants have received major surgery, they must have recovered adequately from the toxicity and/or complications from the intervention prior to starting study treatment.

14. Has received prior palliative radiotherapy within 2 weeks of start of study treatment. Participants must have recovered from all radiation-related toxicities, not require corticosteroids, and not have had radiation pneumonitis.

15. Has received prior therapy with epacadostat or any IDO1 inhibitor, an anti-PD-1, anti-PD-L1, or anti PD-L2 agent, or any agent directed to another stimulatory or co-inhibitory T-cell receptor (eg, CTLA-4, OX-40, CD137).

16. Has received a live vaccine within 30 days prior to the first dose of study treatment. Examples of live vaccines include, but are not limited to, the following: measles, mumps, rubella, varicella/zoster (chicken pox), yellow fever, rabies, Bacillus Calmette–Guérin (BCG), and typhoid vaccine. Seasonal influenza vaccines for injection are generally killed virus vaccines and are allowed; however, intranasal influenza vaccines are live attenuated vaccines and are not allowed.
17. Has received therapy with an MAOI, or UGT1A9 inhibitor within 21 days prior to starting treatment, or anticipates requiring one of these prohibited medications during the treatment phase. Examples of medications in these classes are found in Section 7.7.3.
18. Current use of any prohibited medication as described in Section 7.7.3.

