### 7.2.3 Dose Modifications for Cisplatin or Carboplatin

Investigators may switch participants from cisplatin to carboplatin during the course of the study if toxicities occur. If the cisplatin dose was modified prior to switching, the participant may start at a carboplatin dose of AUC 5 and will be eligible to receive an additional 2 dose modifications of carboplatin.

Table 10 Dose Modification Guidelines for Febrile Neutropenia or Documented Infection

Adverse Event	Number of Occurrences	Treatment Modification
Febrile neutropenia a Documented infection	1	Reduce by 1 dose level The use of growth factors and antibiotics should be considered per local standards
	2	Reduce by 1 dose level Consider prophylactic antibiotics for subsequent cycles. The use of growth factors should be strongly considered per local standards
	3	Discontinue platinum

a ANC <1000/mm^3 ( $1.0 \times 10^9/L$ ) and a single temperature >38.3°C or sustained temperature  $\geq$ 38°C for >1 hour.

Table 11 Dose Modification Guidelines for Platinum Drug-Related Adverse Events

Category	Toxicity	Hold Platinum Treatment for Grade	Timing for Restarting Platinum Treatment	Dose for Restarting Platinum Treatment	Discontinue Platinum
Hematologic	Neutropenia	3 	Neutrophil count resolves to >1,000/mm  (1.0 × 10  /L)	No reduction *consider G-CSF	Toxicity does not resolve within 12 weeks of last infusion or if >2 dose level reductions exceeded
		4 		Reduce by 1 dose level *consider G-CSF	
	Thrombocytopenia	2	Platelet count resolves to ≥75,000/mm  (75 × 10  /L) or baseline	No reduction	
		3-4 		Reduce by 1 dose level	
Nonhematologic	Creatinine increased	2-4 	Toxicity resolves to Grade 0-1	For participants taking Carboplatin, reduce by 1 dose level For participants taking Cisplatin, change Cisplatin to Carboplatin	Toxicity does not resolve within 12 weeks of last infusion or if >2 dose level reductions exceeded
	Ototoxicity or sensory neuropathy	2	Change Cisplatin to Carboplatin May continue treatment with Carboplatin		
		3-4	May switch Cisplatin to Carboplatin if resolved to Grade ≤ 2 within 12 weeks of last infusion If already using carboplatin, then discontinue		

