#### **7.7.4.3 Supportive Care Guidelines for Cisplatin and Carboplatin**

For participants randomized to Group 3 (EXTREME regimen) the use of systemic glucocorticoids during study treatment is acceptable and may be required for premedication.

Please refer to the product label or local standards of care for additional cisplatin and carboplatin supportive measures and AE management.

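### The EXTREME-arm note in Section 7.7.3 accepts live vaccines throughout the study, including the platinum/5-FU cycles

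*Combined protocol and SAP*

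**What the plan says.** Section 7.7.3 lists what participants may not receive during screening and treatment, and its lead-in allows for exceptions stated further down the list. One item bars live attenuated vaccines from 30 days before the first dose and for as long as the participant is in the study. Directly beneath it stands: "Note: For participants randomized to the EXTREME arm the use of live vaccines is acceptable during the study".

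Group 3 receives platinum and 5-FU for up to six 21-day cycles, with weekly cetuximab until progression or unacceptable toxicity (Sections 5.1 and 9.9.2). On the haematological risk of this regimen:

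- Section 3.3.4 cites Grade 3 or 4 neutropenia in 22% of patients in the published EXTREME trial.
- Tables 10 and 12 set dose rules for febrile neutropenia or documented infection under platinum and under 5-FU. At a second occurrence the advice includes "Consider prophylactic antibiotics for subsequent cycles".
- Section 7.7.4.3 adds: "For participants randomized to Group 3 (EXTREME regimen) the use of systemic glucocorticoids during study treatment is acceptable and may be required for premedication".

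Two other provisions mention vaccines. Exclusion criterion 16 in Section 6.2 reads: "Has received a live vaccine within 30 days prior to the first dose of study treatment". Section 7.7 opens with: "Medications or vaccinations specifically prohibited in the exclusion criteria are not allowed during the study".

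**The concern.** The permission is unqualified. A site that reads the note literally may give a live vaccine to a Group 3 participant who is between chemotherapy cycles, neutropenic or taking steroids, and would be within the protocol. What is at stake is participant safety and the clarity of the instruction to sites. No efficacy estimate depends on it.

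**Working it through.** No statistical figure is involved, so the check sets the provisions side by side. The arithmetic concerns only duration and reach.

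**1. Does the permission cover the chemotherapy?** Platinum/5-FU runs for up to 6 cycles x 21 days = 126 days, or 18 weeks, without delays. All of it falls inside the study period that the note covers.

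**2. Does the protocol anticipate immune compromise in that window?** Yes, for the regimen: the 22% neutropenia figure (Section 3.3.4), the febrile-neutropenia and infection rules (Tables 10 and 12), and permitted systemic steroids, for which premedication is the only purpose named (Sections 7.7.3 and 7.7.4.3). Table 11 also lets platinum restart once neutrophils exceed 1,000/mm3, so a count that is acceptable for dosing can still be low.

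**3. Does another provision withdraw the permission during chemotherapy?**

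- Section 9.5.4 requires blood counts to be reviewed before each dose of study treatment. That governs dosing, not vaccination.
- Section 7.7.2 refers to restrictions in the local labels of the study drugs. It does not name vaccines, and the labels are not part of the documents.
- Section 7.7 leaves the final decision on vaccination to the investigator or primary physician. That allows caution but does not require it.

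None of these removes an express statement that live vaccines are acceptable.

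**4. What does the exemption follow?** Compare the neighbouring notes:

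| Restricted item | Arms exempted |
|---|---|
| Coumarin anticoagulants (7.7.2) | EXTREME and pembrolizumab monotherapy |
| MAO inhibitors (7.7.3) | EXTREME and pembrolizumab monotherapy |
| UGT1A9 inhibitors (7.7.3) | EXTREME and pembrolizumab monotherapy |
| Live vaccines (7.7.3) | EXTREME only |

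The first three notes exempt the two arms without epacadostat. The live-vaccine note exempts only the arm without pembrolizumab. The inference, which the protocol does not state, is that the vaccine bar was written with pembrolizumab in mind and waived where that drug is absent. Group 3 receives myelosuppressive chemotherapy instead, and the note does not consider it.

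**5. Reach.**

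- Group 3 size: 89 randomized (Synopsis) x 2/5 = 35.6, about 36. Section 10.9 plans for 36; the actual split is not given.
- Calendar: suppose the last participant was randomized on 02-MAY-2018, the day enrollment stopped, and started treatment 5 days later, the latest allowed. Cycle 1 Day 1 is then 07-MAY-2018. Adding 5 x 21 = 105 days gives Cycle 6 Day 1 on 20-AUG-2018, and 21 more days gives the end of Cycle 6 on 10-SEP-2018. Toxicity holds would extend this.
- The date of Amendment 04 is not visible in the documents, so how much of that window remained is unknown. Live-vaccine use in Group 3 is not reported either.

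**The case against.** The strongest reply is that the safety step is not in the documents. No section says that live vaccines are contraindicated with platinum, 5-FU or cetuximab, and the note permits vaccination without directing it. Sites are repeatedly sent to labels, local standards and physician judgment (Sections 7.7, 7.7.1, 7.7.2 and 7.7.4.3 to 7.7.4.5). With enrollment closed and participants free to leave after the Week 9 scan, the change might reach nobody. The exemption also protects a participant who needs one of the listed vaccines, such as rabies, during chemotherapy.

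Much of this stands. The link from myelosuppression to live-vaccine risk is general clinical reasoning, although its factual premises are all in the protocol. The safeguards are real and make the residual risk small, but they do not cancel an express permission that points the other way.

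Two stronger readings are tempting, and the documents do not support them.

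*A reader might infer a substantive conflict:* that Section 7.7 together with exclusion 16 bars in Group 3 what the note allows. Section 7.7 does say: "If there is a clinical indication for any medication or vaccination specifically prohibited, discontinuation from study treatment may be required". But exclusion 16 is a pre-dose criterion covering 30 days, and the note leaves that period alone. Section 7.7.3 is a subsection of 7.7 and announces its own exceptions. The MAO-inhibitor and UGT1A9 notes exempt arms in the same way although exclusion 17 names both classes without an arm exemption, so the conflict reading would void those notes too. Section 7.7 also stops short of a flat bar: discontinuation is only possible, and the vaccination decision rests with the physician. The general sentence is best read as already qualified by the specific notes. What is missing is a cross-reference.

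*A reader might also turn the 22% into a count of participants at risk:* 0.22 x 36 = 7.9, about 8. That is expected Grade 3 or 4 neutropenia if the cited rate applied here. It is not the number of neutropenic participants given a live vaccine, which the documents do not allow anyone to estimate.

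**Conclusion.** The point holds as a low-priority patient-safety correction. The note accepts live vaccines across the whole of Group 3 participation, including up to 126 days of planned platinum/5-FU for which the protocol itself expects neutropenia and allows steroids, and no other provision clearly withdraws that permission. The number of participants affected is unknown: at most about 36 by allocation, and possibly none if all had finished chemotherapy when Amendment 04 took effect. ORR, its confidence interval and the sample size are unaffected. The conclusion rests on two assumptions: that live vaccines carry added risk during myelosuppressive chemotherapy, which is clinical reasoning from outside the protocol, and that some Group 3 participants could still receive platinum or 5-FU. The cross-reference in Section 7.7 is editorial only.

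**What to change.** Replace the note with wording to this effect: *For participants randomized to the EXTREME arm, live vaccines are prohibited during platinum/5-FU treatment and for an interval after the last platinum or 5-FU dose per local label (sponsor to specify); thereafter they are acceptable subject to local labels.* Notify sites that have Group 3 participants still on treatment. The documents do not supply the interval, so the sponsor must set it.

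As an editorial change, add *except as noted in Section 7.7.3* to the first sentence of Section 7.7. This also aligns the MAO-inhibitor and UGT1A9 notes with exclusion 17.

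The cost is one replaced sentence, one added clause, the IRB/IEC step described in Appendix 3 and a site notice. Data collection and analysis do not change. There is one real downside. Section 7.7.3 ends with a rule that participants who "require the use of any of the aforementioned treatments for clinical management should be removed from the study", and a Group 3 participant who needs a live vaccine during chemotherapy would come under it. Simply deleting the note would be worse, because that rule would then also reach participants on cetuximab alone. Replacement is therefore preferable.

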## 8. Discontinuation/Withdrawal Criteria

### 8.1 Discontinuation of Study Treatment

Discontinuation of study treatment does not represent withdrawal from the study.

As certain data on clinical events beyond study treatment discontinuation may be important to the study, they must be collected through the participant's last scheduled follow-up, even if the participant has discontinued study treatment. Therefore, all participants who discontinue study treatment prior to completion of the protocol-specified imaging requirements (ie, before Week 9 efficacy assessment, PD or initiation of a new anticancer treatment) will still continue to participate in the study as specified in Section 2 and Section 9.9.4.

Participants may discontinue study treatment at any time for any reason or be dropped from the study treatment at the discretion of the investigator should any untoward effect occur. In addition, a participant may be discontinued from study treatment by the investigator or MSD if study treatment is inappropriate, the trial plan is violated, or for administrative and/or other safety reasons. Specific details regarding procedures to be performed at study treatment discontinuation are provided in Section 9.1.10.

A participant must be discontinued from study treatment but continue to be monitored in the study for any of the following reasons:

- The participant or participant's legally acceptable representative requests to discontinue study treatment.
- Radiographic disease progression per RECIST 1.1.
- Unacceptable AEs as described in Section 7.2.1 with a requirement to permanently discontinue.
- The participant interrupts study treatment administration for any TRAE for more than 12 consecutive weeks or more than 3 weeks for interruptions unrelated to AEs, unless approved with written documentation from MSD.
- The participant has a medical condition or personal circumstance which, in the opinion of the investigator and/or MSD, placed the participant at unnecessary risk from continued administration of study treatment.
- The participant has a confirmed positive serum pregnancy test.
- Administrative reasons.
- Any progression or recurrence of any malignancy, or any occurrence of another malignancy that requires active systemic treatment.
- Noncompliance with study treatment or procedure requirements.
- Recurrent Grade 2 pneumonitis.
- Completion of 35 treatment cycles (approximately 2 years) with pembrolizumab plus epacadostat or pembrolizumab monotherapy.

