## 8.2 Withdrawal from the Study

A participant must be withdrawn from the study if the participant or participant's legally acceptable representative withdraws consent from the study.

If a participant withdraws from the study, they will no longer receive study treatment or be followed at scheduled protocol visits.

Specific details regarding procedures to be performed at the time of withdrawal from the study are outlined in Section 9.1.10.

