### **10.5 Analysis Populations**

#### **10.5.1 Efficacy Analysis Population**

The Intention-to-Treat (ITT) population will serve as the population for efficacy analyses. All randomized participants will be included in this population. Participants will be analyzed in the treatment group to which they are randomized.

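### Section 7.7.3 takes participants who need a prohibited therapy out of the study, against Sections 7.7, 8.1 and 8.2; because the list differs by arm, the single ORR scan could be lost in an arm-dependent way.

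*Combined protocol and SAP*

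**What the plan says.** Four sections deal with a participant who comes to need a prohibited therapy.

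- Section 7.7.3 closes its list by saying that participants who, as the investigator sees it, "require the use of any of the aforementioned treatments for clinical management should be removed from the study".
- Section 7.7 is weaker and concerns treatment only: "If there is a clinical indication for any medication or vaccination specifically prohibited, discontinuation from study treatment may be required".
- Section 8.1 states that "Discontinuation of study treatment does not represent withdrawal from the study". It adds that those who stop before the protocol imaging is complete "will still continue to participate in the study as specified in Section 2 and Section 9.9.4".
- Section 8.2 gives withdrawn consent as the only reason for mandatory withdrawal. Of participants who withdraw it says that "they will no longer receive study treatment or be followed at scheduled protocol visits".

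The list in 7.7.3 depends on the arm. On UGT1A9 inhibitors: "For participants randomized to the EXTREME arm or pembrolizumab monotherapy arm, the use of UGT1A9 inhibitors is acceptable". A parallel note frees Groups 2 and 3 from the MAO inhibitor ban. On steroids: "For participants randomized to the EXTREME arm the use of systemic glucocorticoids on study treatment is acceptable and may be required for premedication". Live vaccines are likewise allowed in Group 3 only.

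The efficacy population in 10.5.1 is ITT: "All randomized participants will be included in this population". Section 9.2.1.2 schedules one on-study scan, at Week 9, and Section 10.1 lets the final analysis proceed once each participant has had a post-baseline scan or has left the study.

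**The concern.** Being off treatment and being out of the study have different consequences for the primary endpoint. A participant who is off treatment keeps the Week 9 scan under 8.1. One who is out of the study is no longer followed at scheduled visits. Section 9.1.10 then asks only for the final-visit activities. Under 9.9.4.1 the final visit is the Safety Follow-up Visit, for which the Schedule of Activities mandates no imaging.

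With the arm-specific notes applied, the same new need can have different consequences. A Group 1 participant who needs a UGT1A9 inhibitor (amitriptyline, diclofenac and verapamil are on the list) meets the removal sentence; a Group 2 or Group 3 participant does not. Section 5.4.2 says the monotherapy arm is there to show what epacadostat adds, and the triggers that apply to Group 1 alone fall on that contrast. The glucocorticoid and vaccine triggers fall on Groups 1 and 2 against Group 3.

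At stake is whether some of the non-responders in an arm are in fact participants whose response was never assessed.

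**Working it through.** **The plan's own figures.** Section 10.9 gives Clopper-Pearson 95% limits for 36 and 18 participants. With x responders of n, the limits are the 2.5% quantile of Beta(x, n - x + 1) and the 97.5% quantile of Beta(x + 1, n - x). All ten rows of Tables 19 and 20 reproduce, apart from one rounding difference (11/36, lower limit: 16.347, printed as 16.4). For 14/36 = 38.9% the limits are 23.1 and 56.5, a width of 56.5 - 23.1 = 33.4 points.

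**Triggers by arm (7.7.3, notes applied).**

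| Class | Group 1 | Group 2 | Group 3 |
|---|---|---|---|
| MAO inhibitors | barred | acceptable | acceptable |
| UGT1A9 inhibitors | barred | acceptable | acceptable |
| Systemic glucocorticoids | barred, with exceptions | barred, with exceptions | acceptable |
| Live vaccines | barred | barred | acceptable |
| Radiation, oncologic surgery, other systemic anticancer therapy | barred | barred | barred |

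Group 1 has the most triggers and Group 3 the fewest. The documents give no rate of prohibited-drug use, removal or missing scans for any arm, so the number actually lost cannot be computed.

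**Illustration for Group 1.** Assumptions: n = 36; 14 would-be responders (the row of Table 19 closest to the 39% that Section 3.1 reports for the combination in previously treated participants); a fraction r lost before any post-baseline scan, unrelated to response; and unscanned participants counted as non-responders. The last follows naturally from an ITT denominator, but Section 10 does not state it. Expected ORR = 38.9% x (1 - r).

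| r (assumed) | Expected number lost, 36r | Expected ORR | Shift, points |
|---|---|---|---|
| 0% | 0 | 38.9% | 0 |
| 2% | 0.7 | 38.1% | -0.8 |
| 5% | 1.8 | 36.9% | -1.9 |
| 10% | 3.6 | 35.0% | -3.9 |
| 15% | 5.4 | 33.1% | -5.8 |

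Per person, one would-be responder left unscanned costs 1/36 = 2.8 points in Group 1 and 1/18 = 5.6 points in Group 2. If two would-be responders in Group 1 were lost, the result would be 12/36 = 33.3% (18.6 to 51.0).

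**The case against.** A reader might infer that Group 1 does lose more participants before the scan, that they cannot be responders, and that its ORR is therefore biased downward by some 2 to 6 points (the 5% to 15% rows). The documents do not support that, for these reasons.

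- **Screening removes most foreseeable need.** Exclusion 17 bars, in all arms and before randomization, anyone who took an MAO or UGT1A9 inhibitor within 21 days or expects to need one. Exclusion 18 bars current use of anything prohibited in 7.7.3. For the classes barred in Group 1 alone, only new, unanticipated need over about nine weeks is left.
- **There is another scan.** Section 9.2.1.3 asks for imaging at treatment discontinuation, within 4 weeks either way, for those who stop before Week 9. For someone who stops at Week 5 that window reaches Week 9 (5 + 4). A removed participant can therefore still be a responder if the site obtains this scan.
- **The steroid trigger is narrow.** Section 7.7.3 has exceptions for adverse events, short courses, physiologic doses, inhaled use and allergy prophylaxis, some of them subject to consultation. Steroids and vaccines are also treated alike in Groups 1 and 2, so they do not affect the epacadostat contrast.
- **Other losses are not known.** Participants in every arm may leave early for other reasons, so a longer list does not settle the net direction.
- **The analysis is descriptive.** Sections 10.6.1 and 10.8 plan estimates by arm and no tests.

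Most of this stands, and it limits the size of the problem. It does not remove the contradiction. The discontinuation scan is only a partial safeguard: a participant treated as out of the study may miss it, and it is not mandatory if imaging was done in the previous 4 weeks. Nothing requires that earlier imaging to be post-baseline, so a very early stopper could have only the screening scan.

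**Conclusion.** The contradiction between 7.7.3 and Sections 7.7, 8.1 and 8.2 is plain in the text. Which section a site follows decides whether a participant stays available for the primary-endpoint scan, and the triggers differ by arm. That is a real route to arm-dependent missing response data.

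Its size is unknown and probably small. The range of 0 to about -6 points rests wholly on an assumed loss of 0% to 15% in Group 1, none of those lost being scanned, loss unrelated to response, and unscanned participants counted as non-responders. Its upper end means about 5 of 36 participants newly needing a listed therapy despite exclusions 17 and 18. Even then the shift lies well inside an interval 33.4 points wide. Group 1 is exposed to more triggers; that it loses more participants is not shown.

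The reach is also limited. Enrollment stopped at 89, so for ORR the change helps only participants not yet scanned when it takes effect. The passages should still be reconciled, because the loss is avoidable and bears on the only efficacy endpoint.

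**What to change.** 1. Reconcile 7.7.3 with 7.7, 8.1 and 8.2 so that needing a prohibited therapy does not by itself end study participation. In every arm the participant stays in the study for the Week 9 scan, or the 9.2.1.3 discontinuation scan, and for the Safety Follow-up Visit, unless consent is withdrawn.
2. Treat new anticancer measures on the list (radiation, oncologic surgery, other systemic anticancer therapy) separately, because they change the tumour measurements themselves. Obtain the scan before the measure starts where feasible, and do not count a response first seen afterwards as a response to study treatment. This fits 8.1, which already treats the start of new anticancer treatment as ending the imaging requirement.
3. Beside the ORR, list participants with no post-baseline scan by arm and reason, so that a reader can separate non-response from non-assessment.

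What needing a prohibited therapy means for study treatment is left to the sponsor to reconcile between 7.7 and 7.7.3; no position is taken on it here.

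The cost is a short wording change, one counting rule and one listing. The small downside is that a few scans will be taken in participants who are off treatment or taking a prohibited non-cancer drug.
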